15. Any other medical intervention or condition, which, in the opinion of the PI or treating physician, could compromise patient safety or adherence with the study requirements (including biopsies or leukapheresis procedures) over the primary 3-6 month treatment period.
16. Patients cannot have concurrent enrollment on other phase I, II, or III investigational treatment studies.

17. NOTE: There is no exclusion for prior immune-based therapy. This includes patients previously treated on Arms 1 or 2 who are otherwise eligible for treatment on Arm 3 or 4.

6. Experimental Design

This will be a 1:1 randomized, open-label, single institution pilot trial designed to evaluate the immunological and clinical effect of a DNA vaccine encoding PAP with rhGM-CSF adjuvant given with (concurrently or sequentially) pembrolizumab. Study arms will be defined as follows:

Arm 1: pTVG-HP (100 µg) with rhGM-CSF (208 µg) administered intradermally (i.d.) biweekly 6 times
Pembrolizumab 2 mg/kg, administered intravenously every 3 weeks 4 times, beginning on day 1 after the first pTVG-HP vaccination

Arm 2: pTVG-HP (100 µg) with rhGM-CSF (208 µg) administered intradermally (i.d.) biweekly 6 times
Pembrolizumab 2 mg/kg, administered intravenously every 3 weeks 4 times, the first dose administered two weeks after the last pTVG-HP vaccination

Extended treatment Arm 3:

pTVG-HP (100 µg) with rhGM-CSF (208 µg) administered intradermally (i.d.) every 3 weeks, for a maximum of 16 doses
Pembrolizumab 2 mg/kg, with a maximum dose of 200 mg, administered intravenously every 3 weeks, for a maximum of 16 doses, beginning on day 1 after the first pTVG-HP vaccination

Extended treatment Arm 4:

pTVG-HP (100 µg) with rhGM-CSF (208 µg) administered intradermally (i.d.) every 2 weeks, for a maximum of 24 doses
Pembrolizumab 2 mg/kg, with a maximum dose of 200 mg, administered intravenously every 4 weeks, for a maximum of 12 doses, beginning on day 1 after the first pTVG-HP vaccination

A. Study Arm Assignment and Toxicity Assessment

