Patients with castrate-resistant, metastatic prostate cancer, with evidence of progressive disease by scans (but not by pain symptoms) or rising PSA, who may or may not have been previously treated with other therapies (including chemotherapy, abiraterone, or enzalutamide), will be invited to participate. Subjects will be randomly assigned to a treatment group for the first two study arms. Once at least 12 evaluable subjects have been accrued to Arms 1 and 2, and once Arm 3 is open to accrual, Arms 1 and 2 will be closed and all further accrual will be to Arm 3. Given the absence of significant adverse events observed in previous clinical trials with pTVG-HP, no adverse events > grade 2 are anticipated related to that agent. While not common, previous immune-associated toxicities have been observed with pembrolizumab, including immune-mediated pneumonitis, colitis, hepatitis, hypophysitis, nephritis, hyperthyroidism, and hypothyroidism. Hence these may

be anticipated events. In 89 patients treated with pembrolizumab at 2 mg/kg every 3 weeks in a study of patients with unresectable or metastatic melanoma, < 20% of patients experienced any adverse reaction > grade 2; the most common adverse reaction was fatigue (7% of patients). Three grade 4 laboratory abnormality events (hyperglycemia, increased ALT, and anemia) were reported. In a larger trial of 411 patients with advanced melanoma, 9% of patients discontinued treatment due to adverse reactions. However, patients in the approval trial received a median of 9 doses, more doses than will be used in the current trial. In the current trial patients will be evaluated for evidence of toxicity, and further accrual to a specific treatment arm will be discontinued if the toxicity rate is deemed to be excessive for that arm. Given the more limited exposure to this agent (4 doses total), a toxicity rate of 35% for Grade 3 events or 20% Grade 4 events given an attribution of at least possibly related to study treatment will be considered excessive. Grade 3 limited site reactions (lasting < 48 hours) and fevers/chills (lasting < 48 hours) will be excluded from this assessment, as expected possible adverse events of limited duration from vaccination.

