- G. Immunization #3 - Day 29 (14 +/- 3 days after day 15 visit)
1. Subjects will receive pTVG-HP DNA immunizations intradermally on the deltoid area of the lateral arm (preferentially left arm) with 0.25 mL administered at each of two adjacent sites.
 2. Following vaccinations, the subjects will be observed for 60 minutes for unanticipated adverse events.
- H. Immunization #4 - Day 43 (14 +/- 3 days after day 29 visit)
1. Physical examination, symptoms assessment, and ECOG performance score
 2. Blood draw for CBC, differential and platelets, chemistry panel, PSA and PAP
 3. 10 ml peripheral blood (red-top tubes) for sera to evaluate antibody responses, and 100 ml peripheral blood (green-top heparinized tubes) for T-cell response evaluation and CTC analysis
 4. Subjects will receive pTVG-HP DNA immunizations intradermally on the deltoid area of the lateral arm (preferentially left arm) with 0.25 mL administered at each of two adjacent sites.
 5. Following vaccinations, the subjects will be observed for 60 minutes for unanticipated adverse events.

- I. ARM 1 SUBJECTS ONLY: Anti-PD-1 #3 (Day 43, 1-3 hours after day 43 immunization)
1. Pembrolizumab 2 mg/kg administered intravenously over 30 minutes
 2. Subjects will be observed for additional 30 minutes for unanticipated adverse events. Vital signs (temperature, heart rate and blood pressure) will be assessed and recorded by the staff prior to, and at the end of, the treatment period.
- J. Immunization #5 - Day 57 (14 +/- 3 days after day 43 visit)
1. Subjects will receive pTVG-HP DNA immunizations intradermally on the deltoid area of the lateral arm (preferentially left arm) with 0.25 mL administered at each of two adjacent sites.
 2. Following vaccinations, the subjects will be observed for 60 minutes for unanticipated adverse events.
- K. ARM 1 SUBJECTS ONLY: Anti-PD-1 #4 – Day 64 (7 +/- 3 days after day 57 visit)
1. Physical examination, symptoms assessment, and ECOG performance score
 2. Blood draw for CBC, differential and platelets, chemistry panel, PSA and PAP
 3. Pembrolizumab 2 mg/kg administered intravenously over 30 minutes
 4. Subjects will be observed for an additional 30 minutes for unanticipated adverse events. Vital signs (temperature, heart rate and blood pressure) will be assessed and recorded by the staff prior to, and at the end of, the treatment period.
- L. Immunization #6 - Day 71 (14 +/- 3 days after day 57 visit)

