1. Subjects will receive pTVG-HP DNA immunizations intradermally on the deltoid area of the lateral arm (preferentially left arm) with 0.25 mL administered at each of two adjacent sites.
 2. Following vaccinations, the subjects will be observed for 60 minutes for unanticipated adverse events.
- M. 3-Month Follow-up - Day 85 (14 +/- 3 days after day 71 visit)
1. Physical examination, symptoms assessment, and ECOG performance score.
 2. Blood draw for CBC, chemistry panel, serum PSA and PAP (can be performed +/- 7 days of this visit)
 3. 10 ml peripheral blood (red-top tubes) for sera to evaluate antibody responses, and 100 ml peripheral blood (green-top heparinized tubes) for T-cell response evaluation and CTC analysis (can be performed +/- 7 days of this visit)
 4. CT scan of abdomen and pelvis, bone scintigraphy (can be performed +/- 7 days of this visit, but prior to pembrolizumab treatment for patients in Arm 2)
 5. FLT PET/CT scan (can be performed +/- 7 days of this visit, but prior to pembrolizumab treatment for patients in Arm 2)
 6. Tissue biopsy of same metastatic lesion as in pre-treatment period (can be performed +/- 7 days of this visit, but prior to pembrolizumab treatment for patients in Arm 2)

ARM 2 SUBJECTS ONLY – Anti-PD-1 #1:

7. Pembrolizumab 2 mg/kg administered intravenously over 30 minutes
8. Subjects will be observed for an additional 30 minutes for unanticipated adverse events. Vital signs (temperature, heart rate and blood pressure) will be assessed and recorded by the staff prior to, and at the end of, the treatment period.

N. DAY 106 – (21 +/- 3 days after day 85 visit):

1. Physical examination, symptoms assessment, and ECOG performance score.
2. Blood draw for CBC, chemistry panel, serum PSA and PAP

ARM 2 SUBJECTS ONLY – Anti-PD-1 #2:

3. Pembrolizumab 2 mg/kg administered intravenously over 30 minutes
4. Subjects will be observed for an additional 30 minutes for unanticipated adverse events. Vital signs (temperature, heart rate and blood pressure) will be assessed and recorded by the staff prior to, and at the end of, the treatment period.

O. DAY 127 – (21 +/- 3 days after day 106 visit):

1. Physical examination, symptoms assessment, and ECOG performance score.
2. Blood draw for CBC, chemistry panel, serum PSA and PAP

ARM 2 SUBJECTS ONLY – Anti-PD-1 #3:

3. Pembrolizumab 2 mg/kg administered intravenously over 30 minutes

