This section outlines the statistical analysis strategy and procedures for the study. Prior to the analysis of the final study data, a detailed Statistical Analysis Plan (SAP) will be written describing all analyses that will be performed.

Summary tabulations will be presented that will display the number of observations, mean, standard deviation, median, range, minimum, and maximum for continuous variables and the number and percent per category for ordinal and categorical data. All endpoints of this study will

be presented graphically where possible using boxplots and histograms for continuous variables and (stacked) bar charts for categorical variables. Data analysis will be performed using SAS[®] (SAS Institute Inc., Cary, North Carolina) version 9.3 or greater.

There are many comparisons made between the two trial arms for multiple measurements, both clinical and laboratory. However, since this a pilot study, no adjustment will be made for multiple comparisons. A two-sided test at a significance level of 0.05 will be used for all comparisons, unless noted otherwise.

F.2. Analysis Populations

The ITT population consists of all patients who are randomized. The per-protocol population consists of all evaluable patients, i.e., patients who have been treated according to protocol (all inclusion/exclusion criteria are satisfied, and adequate treatment compliance (complete treatment to at least day 43). The safety population consists of all subjects who received at least one dose of pTVG HP alone or in combination with pembrolizumab. All primary, secondary and correlative outcomes will be analyzed for both the IIT and per-protocol population. The IIT population will be the primary analysis population. Safety will be evaluated using the safety population.

F.3. Baseline Comparability

All measurements (variables) collected at baseline will be summarized and compared between study arms. These include demographic variables, ECOG PS, lab parameters (CBC, chemistry panel, serum testosterone, PSA and PAP) medical history information and CTCs. Comparisons between study arms of baseline variables on a continuous scale will be performed using a two-sample t-test and/or nonparametric Wilcoxon Rank Sum test. Comparisons between study arms of baseline variables on a categorical scale will be performed using Fisher's exact test.

F.4. Analysis of Primary Endpoints

F.4.1. Analysis of Toxicity Rates and Serum Chemistry Parameters

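### The per-protocol rule stops at Day 43, 42 days before Arm 2's first pembrolizumab dose, so an Arm 2 patient given vaccine alone can count as treated with the sequence

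*Combined protocol and SAP*

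**What the plan says.** Section 11.F.2 equates the two terms: "The per-protocol population consists of all evaluable patients, i.e., patients who have been treated according to protocol". Compliance is met by "adequate treatment compliance (complete treatment to at least day 43". No arm-specific threshold is given, and no pembrolizumab dose is required in Arm 2. The same section makes ITT the primary population and repeats all primary, secondary and correlative outcomes in the per-protocol set.

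Section 6 starts pembrolizumab on day 1 in Arm 1. For Arm 2 it has "the first dose administered two weeks after the last pTVG-HP vaccination". Section 9 lists Arm 2's first infusion under "3-Month Follow-up - Day 85 (14 +/- 3 days after day 71 visit").

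Safety uses a separate set: "The safety population consists of all subjects who received at least one dose of pTVG HP alone or in combination with pembrolizumab". Section 11.F.4.1 then reports toxicity rates for each arm, while primary objective 1 concerns the safety of the two agents in combination.

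The word evaluable also governs closure of the randomized arms in Section 6.A: "Once at least 12 evaluable subjects have been accrued to Arms 1 and 2". Section 11.F.2 holds the only general definition of that word.

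**The concern.** The randomized question is concurrent versus sequential pembrolizumab. A per-protocol analysis is meant to show outcomes in patients who received their assigned regimen. In Arm 1 the Day 43 rule secures substantial exposure to both agents. In Arm 2 it secures exposure to the vaccine only.

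Stopping between Day 43 and Day 85 is foreseeable. Section 6.B allows it for undue toxicity, for symptomatic progression, or at the discretion of patient and physician. Such a patient would stay in Arm 2's per-protocol results as a recipient of the sequence. The same patient stays, properly, in Arm 2's all-treated toxicity denominator. A reader who takes that rate as the toxicity of the combination would not know how many patients never received the second agent.

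**Working it through.** **1. Exposure at the threshold.** Scheduled days from Section 9 and the treatment calendars:

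- Vaccine, both arms: Days 1, 15, 29, 43, 57, 71. The fourth is "Immunization #4 - Day 43 (14 +/- 3 days after day 29 visit").
- Pembrolizumab, Arm 1: Days 1, 22, 43, 64. The third is "ARM 1 SUBJECTS ONLY: Anti-PD-1 #3 (Day 43, 1-3 hours after day 43 immunization").
- Pembrolizumab, Arm 2: Days 85, 106, 127, 148.

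| By Day 43 | Arm 1 | Arm 2 |
|---|---|---|
| Vaccinations | 4 of 6 | 4 of 6 |
| Pembrolizumab doses | 3 of 4 | 0 of 4 |

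Gap to Arm 2's first dose: 85 − 43 = 42 days. Three visit intervals of 14 ± 3 days lie between, so the gap is 42 ± 9, or 33 to 51 days.

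Section 11.C gives Arm 2 pembrolizumab biweekly 6 times, against every 3 weeks 4 times in Section 6. The two must be reconciled. Both place the first dose two weeks after the last vaccination, so the gap and the count of zero doses at Day 43 do not change.

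**2. The plan's sample size.** Section 11.E proposes 15 per arm for 80% power, Fisher's exact test, one-sided 0.10. Enumerating both binomial distributions gives a smallest n of 15 per arm for 25% vs 70% (power 82.3%) and for 20% vs 65% (power 82.7%). The arithmetic reproduces; the issue is who counts as evaluable, not the number.

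**3. How many patients could be concerned.** The documents give no Day 43 to 85 drop-out rate. Let d be an assumed fraction of 15 Arm 2 patients. Expected number = 15d; chance of at least one = 1 − (1 − d)^15.

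| d (assumed) | Expected number | Chance of at least one |
|---|---|---|
| 5% | 0.75 | 53.7% |
| 10% | 1.5 | 79.4% |
| 20% | 3.0 | 96.5% |
| 30% | 4.5 | 99.5% |

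For scale, Section 11.E allows for 1 unevaluable patient of 16 per arm: 1/16 = 6.25%.

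**4. Toxicity rate, illustration only.** Let u be the share of Arm 2's safety set given no pembrolizumab, including anyone who stopped before Day 43. Reported rate = (1 − u) × rate in exposed patients + u × rate in unexposed patients. With an assumed 30% in exposed and 0% in unexposed patients, u = 10% gives 0.90 × 30% = 27%, and u = 30% gives 0.70 × 30% = 21%. Section 6.A anticipates no vaccine-related events above grade 2, which makes a low second term plausible for grade 3 or higher. It is not certain: a patient who stops because of toxicity on vaccine alone adds an event.

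**5. Cost of a later landmark.** Exact power at 25% vs 70%, Arm 1 held at 15:

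| Arm 2 n | 15 | 14 | 13 | 12 | 11 | 10 |
|---|---|---|---|---|---|---|
| Power | 82.3% | 85.1% | 78.3% | 77.9% | 74.4% | 71.8% |

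The rise at 14 reflects the discreteness of Fisher's test. Losses from Arm 1 would lower these figures further.

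**The case against.** **Reach.** ITT is primary and rightly keeps Arm 2 patients who stop before pembrolizumab, so the main comparison stands. Day 43 is itself a common landmark: both arms have 4 of 6 vaccinations, and an early cut brings little selection after randomization. This is correct and limits the point to supportive analyses. It does not make a vaccine-only patient a recipient of the sequence.

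**Safety set.** Admission on one vaccine dose is an ordinary all-treated rule, it states the vaccine-alone case openly, and it does not use Day 43. This also stands. The gap is only the absence of an exposed-patient rate beside it.

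**Size.** Early stopping may be rare. Progression on the Month 3 scan does not by itself end treatment, stopping for PSA rise alone is discouraged, a life expectancy of at least 6 months is required, and rapidly progressive symptomatic disease is excluded. The true number could be zero; the documents do not settle it.

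**A later landmark has its own bias.** Before Day 85 only Arm 1 is exposed to pembrolizumab toxicity, and Section 8 requires holds, skipped doses and cessation. A strict as-scheduled rule would drop Arm 1 patients who were managed exactly as planned. It would also remove deaths before Day 85, which are events in time to progression from randomization. These objections shape the fix.

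**Stronger readings that the documents do not support.** A reader might infer that the per-protocol comparison says nothing about concurrent versus sequential treatment. In fact only some Arm 2 patients, of unknown number, may be vaccine-only. A reader might also infer that Arms 1 and 2 closed with fewer than 12 patients who received the sequence in Arm 2. The definition permits that, but no count is given. Section 2.F shows 11 patients already on Arm 3 by January 2018, so changing the definition now cannot alter that closure.

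**Conclusion.** The mismatch is certain from the schedule. The threshold falls 42 days before Arm 2's first scheduled pembrolizumab dose, and at that point exposure is 3 of 4 doses in Arm 1 and 0 of 4 in Arm 2. Nothing elsewhere in the documents repairs it.

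The consequence is limited. The primary ITT result is untouched. The per-protocol analyses, and the reading of Arm 2's toxicity rate as a combination rate, are affected by an amount the documents do not give. The patient counts and the 21% to 27% illustration rest wholly on assumed rates. The sponsor can replace them with the actual number of Arm 2 patients who received no pembrolizumab.

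This is worth settling in the detailed SAP that Section 11.F.1 says will be written before the final analysis.

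**What to change.** 1. **Safety.** Keep the all-treated safety set. Beside it report Arm 2 toxicity among patients with at least one pembrolizumab dose. State how many Arm 2 patients received none, and how many of those were counted as evaluable.

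2. **Per-protocol set, Arms 1 and 2.** Keep ITT primary. In Section 11.F.2 use one landmark for both arms: on study and treated per protocol through the Day 85 visit, with the first pembrolizumab dose given in Arm 2.
   - Count holds and skipped doses made under Section 8's toxicity rules as compliant.
   - Label the analysis supportive, because it conditions on events after randomization.
   - Report exclusions by arm and reason, including deaths before Day 85.
   - Show the Day 43 set as a sensitivity analysis. The change would come after open-label results were seen: Section 2.F already cites PSA decline in 8 of 13 Arm 1 patients.

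3. **No separate Arm 2-only definition of evaluable.** It would remove early stoppers from one arm and leave them in the other.

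Day 85 already serves in the plan as the second baseline for progression (Section 11.F.4.2), so no visit or procedure changes.

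The cost is SAP wording, one toxicity column and a smaller per-protocol set. If 20% of 15 Arm 2 patients stopped between Day 43 and Day 85 (an assumption), 3 would be lost; power of the per-protocol comparison at 25% vs 70% would then be 77.9% rather than 82.3%, before any Arm 1 losses. Some selection remains, which the primary ITT analysis avoids.

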The expected 6-months progression-free survival rate in Arm 2 (pembrolizumab is administered sequentially after pTVG-HP) is 25%. It is hypothesized that the treatment of pTVG-HP, when administered concurrently with pembrolizumab (Arm 1), will result in a substantial increase in the 6-month progression-free survival rate. Specifically, it is anticipated that the 6-month progression-free survival rate in Arm 1 will be at least 65-75%. The following table shows the required sample sizes for detecting various differences in the 6-month progression-free survival rates between the two study arms, assuming 80% power and a one-sided 0.10 significance level. Since this is a pilot study, a less stringent significance level of 0.10 rather the traditional 0.05 level will be used for the primary efficacy evaluation.

	6-month progression free survival rate Arm 1			
6-month progression free survival rate Arm 2	0.65	0.70	0.75	0.80
0.20	15	11	10	9
0.25	17	15	11	10

A sample size of 15 patients per arm is proposed. This sample size will provide 80% power to detect an anticipated absolute difference of at least 45% (e.g., 25% vs. 70% or 20% vs. 65%) in the 6-months progression free survival rates between the two arms. These calculations are based on Fisher’s exact test. Furthermore, the proposed sample size of 15 patients per arm is also sufficient to provide accuracy in estimating toxicity rates. Specifically, the toxicity rates (i.e., of grade ≥ 2, grade ≥ 3, grade 4 toxicities) for each arm will be estimated with a standard error of less than 15% and the 95% confidence interval of the toxicity rates will be no wider than 45%. The probability of observing at least one event of a serious adverse event within a study arm is >95% if the adverse event rate is 20%. Analogously, the probability of observing at least one event of serious adverse event is at least 79% if the adverse event rate is only 10%.

In order to account for unevaluable (for efficacy evaluation) patients, 32 eligible patients (16 per arm) will be accrued and randomized. Based on past experience with this patient population treated at our institution, we anticipate that the proposed total number of 32 patients will be accrued within 18 months.

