Subjects will be evaluated at each visit by a review of systems based on the most recent version of the NCI common toxicity criteria. Furthermore, serum chemistries, including renal function tests, blood counts, liver function tests, and serum amylase, will be evaluated at 6-12 week intervals. Toxicities will be summarized by type and severity in tabular format. Toxicity rates (grade 2, grade 3, grade 4, grade ≥ 2 , grade ≥ 3 , etc.) will be calculated for each study arm and reported along the corresponding 95% confidence intervals. The 95% confidence intervals will be constructed using the Wilson score method. Fisher's exact test will be used to compare toxicity rates between study arms. Serum chemistry and amylase parameters will be summarized using standard descriptive statistics. Changes from the baseline assessment will be evaluated using a paired t-test.

F.4.2. 6-Month Progression Free Survival Rate and Median Time to Radiographic Progression

The 6-month progression-free survival rate, along with the corresponding two-sided 95% confidence intervals, will be reported for each arm, and for the overall combined study. The Wilson

score method will be used to construct the confidence intervals. Fisher's exact test will be used to compare the 6-month progression-free survival rates between study arms.

Median time to radiographic progression will be estimated for each arm using the Kaplan-Meier method. The median time to radiographic progression will be reported for each of the four arms along with the corresponding 95% confidence intervals which will be constructed using the Brookmeyer-Crowley method. The log-rank test will be used to perform the comparison of time to radiographic progression between Arm 1 versus Arm 2. A one-sided 0.10 significance level will be used to conduct the comparison of the 6-month progression-free survival rate and time to radiographic progression between study arms. Within Arm 3 and Arm 4, the null hypothesis that the median time to radiographic progression is at most 3 months will be tested against the alternative hypothesis that the median time to radiographic progression is greater than 3 months.

In order to evaluate the 6-month progression-free rate and median time to radiographic progression as a function of baseline time point (pretreatment or 3-months post treatment, the analysis will be conducted using two different baseline values: (1) Date of randomization, and (2) 3-months disease assessment.

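### Fisher's exact test leaves about half of the one-sided 0.10 level unused in the Arm 1 v Arm 2 six-month PFS comparison; Boschloo's exact test would recover power at almost no cost if fixed before the comparison is seen

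*Combined protocol and SAP*

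**What the plan says.** All references are to the combined protocol and SAP.

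- **Section 11.E (sample size).** The table of sample sizes is built "assuming 80% power and a one-sided 0.10 significance level". The reason given is that, in a pilot, "a less stringent significance level of 0.10 rather the traditional 0.05 level will be used for the primary efficacy evaluation". "A sample size of 15 patients per arm is proposed", justified by 80% power for 25% v 70% or 20% v 65%, and the calculation is stated to rest on Fisher's exact test. Sixteen per arm are to be randomized, to allow for unevaluable patients.
- **Section 11.F.4.2 (analysis).** Fisher's "exact test will be used to compare the 6-month progression-free survival rates between study arms". On the level: "A one-sided 0.10 significance level will be used to conduct the comparison of the 6-month progression-free survival rate". This overrides the two-sided 0.05 default of Section 11.F.1.
- **Section 6.A (closing the arms).** "Once at least 12 evaluable subjects have been accrued to Arms 1 and 2", and once Arm 3 is open, the two randomized arms close. Section 2.F makes clear that the 12 is per arm.
- **Sections 11.F.1 and 11.F.2.** A detailed SAP is to be written before the final data are analysed. The ITT set, all randomized patients, is primary.

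The documents do not discuss how conservative Fisher's test is, mention an unconditional exact test, or restate power at 12 per arm.

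**The concern.** The sponsor accepted a 10% one-sided false-positive risk in order to gain power in a small trial. Fisher's test conditions on the total number of patients progression-free at six months. With about 15 per arm, few p-values are attainable for any given total, and the largest one not above 0.10 is usually well below it. The test therefore runs at roughly half the risk that the plan accepted, and the unused part is power lost.

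This matters because six-month PFS is a primary endpoint and sizes the randomized part of the trial, and because the arms may close with fewer than the 15 per arm for which power was worked out.

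**Working it through.** **Inputs.** Fisher's test, one-sided 0.10, 15 per arm, 25% v 70% and 20% v 65%, 16 per arm randomized (Section 11.E); test and level at analysis (Section 11.F.4.2); at least 12 evaluable per arm at closure (Sections 2.F and 6.A). The 13 v 12 case is an illustration: Section 2.F mentions 13 patients in Arm 1, and 12 is the minimum for Arm 2.

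**Formulas.** Let x of n1 (Arm 1) and y of n2 (Arm 2) be progression-free at six months, with t = x + y.

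- Fisher's one-sided p(x, y) = sum over k ≥ x of C(n1, k)·C(n2, t − k) / C(n1 + n2, t). Reject if p ≤ 0.10.
- Power = sum over the rejection region of Bin(x; n1, p1)·Bin(y; n2, p2).
- Maximum size = the largest value of that sum over all common rates p1 = p2.
- Boschloo: use Fisher's p as the test statistic, and take the largest cutoff for which the maximum size is still ≤ 0.10.

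**Step 1: the plan's own figure.** Enumerating every table, the smallest n with at least 80% Fisher power is 15 for 25% v 70% (82.3%) and 15 for 20% v 65% (82.7%), as stated. Seven of the eight cells of the 11.E table reproduce directly. The eighth, 20% v 80%, is printed as 9 and depends on ties. At 8 per arm the tables 3 v 0 and 8 v 5 have p exactly 0.10. Counted as rejections, power is 80.1%. Each tied table has probability 56 × 0.8³ × 0.2⁵ × 0.8⁸ = 0.0015 under 20% v 80%, so excluding both gives 79.8%, and the printed 9 follows. Nothing below depends on this cell.

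**Step 2: why the level is not used.** Take 15 per arm and 4 progression-free in Arm 2. Nine in Arm 1 gives p = 8,348,445 / 119,759,850 = 0.070. Eight gives p = 11,397,295 / 86,493,225 = 0.132. Fisher needs nine. Gaps of this kind run through the table, so the maximum size is 0.0495 (at a common rate of 0.50), and 0.042 at the planned 25%. Boschloo's cutoff at 15 per arm is 0.132, which admits the 8 v 4 table.

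**Step 3: both tests, 25% v 70%.**

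| Arm 1 / Arm 2 | Fisher max size | Fisher power | Boschloo max size | Boschloo power | Gain (points) |
|---|---|---|---|---|---|
| 11 / 11 | 0.067 | 76.2% | 0.078 | 76.5% | 0.3 |
| 12 / 12 | 0.0495 | 70.0% | 0.081 | 81.1% | 11 |
| 13 / 12 | 0.055 | 77.0% | 0.096 | 84.4% | 7 |
| 13 / 13 | 0.038 | 73.2% | 0.085 | 85.0% | 12 |
| 14 / 14 | 0.044 | 78.2% | 0.093 | 88.1% | 10 |
| 15 / 15 | 0.0495 | 82.3% | 0.082 | 86.2% | 4 |
| 16 / 16 | 0.055 | 85.7% | 0.095 | 90.7% | 5 |

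In every row Boschloo's region contains Fisher's. A standard library routine for Boschloo's test gave the same 81.1% at 12 per arm.

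**Step 4: other scenarios.** For 20% v 65%, power goes from 72.3% to 81.8% at 12 per arm and from 82.7% to 88.0% at 15. For 25% v 65%, the low end of the range anticipated in 11.E, it goes from 73.2% to 79.1% at 15 and from 77.3% to 84.7% at 16.

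**The case against.** **The plan is consistent and its claim is true.** Design and analysis use the same test at the same level, and 15 per arm gives the stated power. A significance level is a ceiling, not a budget that must be spent, and conditional against unconditional exact testing is a choice between valid methods. All of this stands. A reader might infer that the sample size is wrong or that the plan breaks its own level; the documents support neither. Boschloo does not spend the full 0.10 either.

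**The gain depends on n.** Fisher's power is saw-toothed: it falls from 76.2% at 11 per arm to 70.0% at 12. A reader might take the 11 points at 12 per arm as the general gain, or take Fisher's true error to be below 0.05 throughout. Neither holds. At the planned 15 to 16 per arm the gain is 4 to 5 points, at 11 it is almost nothing, and Fisher's maximum size exceeds 0.05 at 16 per arm and at 13 v 12. Twelve evaluable is also a minimum for closing the arms, not the planned number for the primary ITT analysis.

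**Timing.** The trial is open-label, and this version already describes outcomes in the randomized arms: some PSA decline in 8 of 13 Arm 1 patients (Section 2.F), and responses followed by progression (Section 11.C). Boschloo rejects 8 more tables than Fisher at 15 per arm and 7 more at 12. Adopting it after seeing the PFS comparison would loosen a primary criterion with knowledge of the data. This stands, and it governs the fix. The documents do not show that the six-month PFS comparison itself has been seen.

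**Multiplicity.** Section 11.F.4.2 also runs the PFS comparison from a second baseline and adds a log-rank test at 0.10, and Section 11.F.1 makes no adjustment, so conservatism in one test may look welcome. But the plan sets 0.10 for each comparison openly. If a tighter overall error rate were wanted, it should be set as such and not left to the discreteness of one test.

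**Conclusion.** The point holds as a cheap improvement, not as an error. Fisher's test at nominal one-sided 0.10 has a maximum true error of about 4% to 5.5% at 12 to 16 per arm, so about half of the deliberately relaxed level goes unused. Boschloo's test keeps exact size at or below 0.10 and, for 25% v 70%, adds 4 to 5 points of power at 15 to 16 per arm and about 7 to 12 points at the 12 to 14 per arm that could result if the arms close early. At 12 to 14 per arm Fisher falls short of 80% and Boschloo does not.

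This rests on independent binomial outcomes, the rates in Section 11.E, every analysed patient being classified at six months, and the test being fixed before the comparison is seen.

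**What to change.** In the detailed SAP promised in Section 11.F.1, and in Section 11.F.4.2 if it is amended:

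1. Name Boschloo's unconditional exact test at one-sided 0.10 for the Arm 1 v Arm 2 six-month PFS comparison, with Fisher's p-value reported alongside.
2. Name the software. Section 11.F.1 specifies SAS, so confirm that the version in use provides the test, or name another package.
3. Date and document the change as made before the arms' six-month PFS was compared. If that comparison has already been seen, keep Fisher as primary and report Boschloo as a labelled sensitivity analysis.

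The cost is a short SAP entry. It needs no extra patients, no new endpoint and no change to the sample size. The statistical price is that the maximum type I error rises from about 5% to about 8% to 10%, within the level the plan already accepts.
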